8.2 Deaths, Serious Adverse Events and other Significant Adverse Events

All deaths, AEs and other significant AEs will be listed.

8.3 Pregnancies

Pregnancy will not be classified as SAE except in cases where it can be shown that the effectiveness of the contraception was affected by the IMP/RP. All pregnancy cases except those emerging after 80 days (66 days per exclusion criteria and 14 days additional waiting period) after the last treatment cycle in the PRRT group, and 70 days (56 days per exclusion criteria and 14 days additional waiting period) after treatment in the everolimus group, will be monitored and followed up in regular intervals in order to identify adverse events especially fulfilling the criteria for a SAE.

8.4 Clinical Laboratory Evaluations

Haematology: haemoglobin, haematocrit, mean corpuscular volume (MCV), mean corpuscular haemoglobin (MCH), white blood cell count (total and differential: leukocytes, neutrophils, eosinophils, basophils, lymphocytes, monocytes), red blood cells, platelets.

Biochemistry: sodium, potassium, chloride, calcium, glucose, creatinine, urea, albumin, total bilirubin, aspartate transaminase (AST), alanine transaminase (ALT), alkaline phosphatase (AP), gamma-glutamyl transferase (GGT), lipase, amylase, total protein,.

Clotting parameters: prothrombin time (quick), reagent-independent prothrombin ratio (international normalised ratio; INR), activated partial thromboplastin time (aPTT).

Urinalysis: specific gravity, pH, protein, glucose, blood, leukocytes, ketones, nitrite, albumin, creatinine; α -1-microglobulin will also be tested in urine but only in centres with adequate technical equipment and an established test method.

Tumour markers: Chromogranin-A, further markers

All lab parameters will be summarised by visit and treatment arms as continuous data (raw and change from baseline) or category data where appropriate (e.g. urine test with category units).

The following parameters will also be presented as boxplot graphs by visit and treatment arm: WBC, RBC, HB, Neutrophils, Lymphocytes, Platelets, alkaline phosphatase, bilirubin, AST, ALT, albumin, potassium, sodium, calcium, and tumour markers.

For the following parameters the percentage of patients experiencing CTCAE toxicity will also be summarised by worst CTCAE grades (all grades pooled and Grades 3 and 4 pooled) and by treatment arm for baseline and post first IMP dosing parts of the study:

ITM-LET-01	Statistical Analysis Plan
------------	---------------------------

Table 6: List of laboratory parameters to be analysed according to CTCAE guidelines

Lab parameter	CTCAE term:
Lymphocytes	Lymphocyte count increased
	Lymphocyte count decreased
Hb	Anaemia
Leukocytes	Leukocytosis
	White blood cell decreased
Platelets	Platelet count decreased
PNN	Neutrophil count decreased
Creatinine	Creatinine increased
Fasting blood glucose	Hypoglycaemia
	Hyperglycaemia
Calcium	Hypocalcaemia
	Hypercalcaemia
Potassium	Hypokalaemia
	Hyperkalaemia
Sodium	Hyponatremia
	Hypernatremia
GGT	GGT increased
Alkaline Phosphatase	Alkaline Phosphatase increased
AST	AST increased
ALT	ALT increased
Total bilirubin	Blood bilirubin increased
Albumin	Hypoalbuminemia

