18. Serious non-malignant disease (e.g. psychiatric, infectious, autoimmune or metabolic), that may interfere with the objectives of the study or with the safety or compliance of the subject, as judged by the investigator
19. Clinically relevant renal, hepatic, cardiovascular, or haematological organ dysfunction, potentially interfering with the safety of the study treatments, as follows:
- Renal
    - Renal obstruction
  - Hepatic
    - Total bilirubin >1.5 x ULN
    - AST or ALT >2.5 x ULN
    - Alkaline phosphatase >5 x ULN
    - Albumin <3 g/dL, unless prothrombin time is within normal range
  - Cardiovascular
    - New York Heart Association classification III and IV
    - Uncontrolled hypertension
  - Haematopoietic
    - Platelets  $\leq 80 \times 10^9/L$
    - Absolute neutrophil count (ANC)  $< 1 \times 10^9$  cells/L
20. Pregnant (see Section 8.3.6) or breast-feeding women. Female patients of childbearing potential or male patients with female partners of childbearing potential, unless willing to practice full and true sexual abstinence or who are surgically/permanently sterile (bilateral tubal occlusion, hysterectomy, or vasectomy), or female patients whose male partners have medically successful vasectomy (provided the partner is the sole sexual partner of the female patient of childbearing potential), or who are not willing to practice highly effective contraception in combination with a barrier method of contraception (e.g. condom). Contraception methods that are considered highly effective are: oral or non-oral (injected or implanted) non-oestrogen progesterone-based hormonal method; oral, intravaginal, or

transdermal combined oestrogen and progesterone-based hormonal method; and/or intrauterine device (IUD), and/or intrauterine hormone-releasing system (IUS). Sexual abstinence or the contraception methods described above must be followed throughout the entire study period and for 56 days after treatment in the everolimus group and, 66 days in the PRRT group (10 half-lives of  $^{177}\text{Lu}$ ) after the last treatment cycle (see Section 8.3.1.1).

21. Subjects not able to declare meaningful informed consent on their own (e.g. with legal guardian for mental disorders) or any other vulnerable population to that sense (e.g. persons institutionalised, incarcerated etc.)

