#### Adverse event (AE)

Any untoward medical occurrence in a patient or clinical investigation subject administered a pharmaceutical product and which does not necessarily have a causal relationship with this treatment. An AE can therefore be any unfavourable and unintended sign (including an abnormal laboratory finding), symptom, or disease temporally associated with the use of a medicinal (investigational) product, whether or not considered related to the medicinal (investigational) product.

By definition, for this study, all AEs are regarded as 'treatment emergent', i.e., not seen before treatment or, if already present before treatment, worsened after start of treatment. See Section [8.3.2.6](#) for exemptions.

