5.6 Baseline Definition

Unless stated otherwise:

- for demographic parameters, tumour assessment, QoL, biomarkers and in general all efficacy related variables, baseline is defined as the last non-missing measurement on or prior to randomisation date.
- for lab, vital signs and in general all safety related variables, baseline is defined as the last non-missing measurement prior to first dosing of study treatment.

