8.5 Other Safety Measures

- Tubular extraction rate (TER):

Relative change from baseline by treatment arm and by visit.

Box plot of raw data by visit and by treatment arm.

- Glomerular filtration rate (GFR)

GFR will be calculated based on the CKD-EPI equation (2021):

$$\text{GFR} = 142 * \min(\text{Scr}/\kappa, 1)^{\alpha} * \max(\text{Scr}/\kappa, 1)^{-1.200} * 0.9938^{\text{Age}} * [1.012 \text{ if female}]$$

Scr is serum creatinine in mg/dL, κ is 0.7 for females and 0.9 for males, α is -0.241 for females and -0.302 for males, min indicates the minimum of Scr/ κ or 1, and max indicates the maximum of Scr/ κ or 1.

Relative change from baseline by treatment arm and by visit.

Box plot of raw data by visit and by treatment arm.

- Renal volume (V_{kidney})

Relative change from baseline by treatment arm and by visit.

Box plot of raw data by visit and by treatment arm.

- Frequency of occurrence and severity of abnormal findings in safety investigations:
 - vital signs:

Vital signs include heart rate, temperature, systolic and diastolic blood pressures and weight measurement.

The BMI will be derived from the collected vital signs using the following formula: $\text{BMI} = \text{weight} / \text{height}^2$

In addition to summary table for continuous data (change from baseline), box plots by visits will be generated for all vital signs as well as for variables derived from vital signs (e.g. BMI) by treatment arm.

- 12-lead ECG

ECG parameters will be presented by visit and treatment arm as continuous data (change from baseline) and also classified as follows:

QTc Absolute count

Post-administration value > 500 ms when not present at baseline (new onset)

Post-administration value of > 480 and ≤ 500 ms when not present at baseline (new onset)

Post administration value of > 450 and ≤ 480 ms when not present at baseline (new onset)

Other

QTc Change from baseline:

Change in QTc from baseline of > 30 and ≤ 60 ms

Change in QTc from baseline > 60 ms

Other

PR

ITM-LET-01	Statistical Analysis Plan
-------------------	----------------------------------

PR relative change from baseline of more than 25% increase leading to PR > 200 ms

Other

QRS

QRS relative change from baseline of more than 25% increase leading to QRS > 120 ms

Other

HR

HR relative change from baseline of more than 25% increase leading to HR > 100 bpm

HR relative change from baseline of more than 25% decrease leading to HR < 50 bpm

Other

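### The laboratory toxicity table in SAP 8.4 does not link post-dose grade to the patient's own baseline grade, so unchanged entry abnormalities count as toxicity and any-grade risk ratios are pulled towards 1

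*SAP*

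**What the plan says.** SAP 8.4 lists the laboratory parameters to be graded in its Table 6 and states: "For the following parameters the percentage of patients experiencing CTCAE toxicity will also be summarised by worst CTCAE grades". Two pools are planned, all grades together and grades 3 and 4 together. The sentence ends "and by treatment arm for baseline and post first IMP dosing parts of the study", so baseline grades are also shown by arm. All laboratory parameters are additionally summarised by visit and arm, as raw values and as change from baseline.

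The visible SAP text has no condition that the post-dose grade must be new or worse than at baseline. It also has no cross-tabulation of baseline grade against worst post-dose grade.

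The rest of the plan does refer safety findings to baseline:

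- SAP 5.6 fixes the safety reference: "baseline is defined as the last non-missing measurement prior to first dosing of study treatment".
- Protocol 8.3.2.1 treats adverse events as treatment-emergent, meaning "not seen before treatment or, if already present before treatment, worsened after start of treatment".
- SAP 8.5 counts QTc categories only when they were absent at baseline, and bases the PR, QRS and heart-rate categories on relative change from baseline.

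Protocol 4.2.2 admits patients with abnormal values. Exclusion for alkaline phosphatase, for example, starts only at "Alkaline phosphatase >5 x ULN".

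**The concern.** The percentage is labelled as patients experiencing toxicity, and a reader will take it as something that happened on treatment. Followed as written, it mixes patients who worsened with patients who simply stayed as they were at entry.

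This matters because the population can enter with abnormal laboratory values, and hepatic tumour burden of up to 70% is allowed. If many patients in both arms already carry an abnormality, the any-grade percentages are high in both arms and their ratio moves towards 1, whatever the treatments do. Two separate percentages for before and after dosing cannot be unpicked. A row showing 40% at baseline and 45% after dosing is compatible with 5% new cases, or with many more if some baseline abnormalities resolved.

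All-grade pooling has a second consequence: a patient who moves from grade 1 to grade 2 contributes nothing visible to the any-grade row.

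**Working it through.** The documents give no rate, test or power for this table, so there is no planned figure to reproduce. I checked two things: which parameters are exposed, and what the counting rule does to an arm comparison.

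**Which parameters are exposed.** Sources are the exclusion criteria in Protocol 4.2.2, the grading in Protocol Table 9, and the parameter list in SAP Table 6.

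| Parameter | Numeric entry limit | Consequence at screening |
|---|---|---|
| Alkaline phosphatase | excluded above 5 x ULN | values well above normal admitted |
| AST, ALT | excluded above 2.5 x ULN | values above normal admitted |
| Total bilirubin | excluded above 1.5 x ULN | values above normal admitted |
| Neutrophils | excluded below 1 x 10^9/L | Table 9 puts grade 3 below 1, so no grade 3-4; grade 2 admitted |
| Platelets | excluded at or below 80 x 10^9/L | Table 9 puts grade 2 below 75, so no grade 2 or higher |
| GGT, haemoglobin, lymphocytes, glucose, electrolytes | none listed | any grade possible |

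Exposure is therefore mainly in the any-grade rows, and in parameters with a loose limit or none.

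**Effect on the comparison.** Let b be the share of patients already abnormal at baseline, equal in both arms and with every abnormality persisting. Let p be the incidence of new toxicity among the rest. Then:

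- rate under the SAP 8.4 rule = b + (1 - b)p
- treatment-emergent rate over all patients = (1 - b)p
- treatment-emergent rate among patients normal at entry = p

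Both b and p are assumptions. I take p = 10% in one arm and 22% in the other, so the true risk ratio is 22/10 = 2.20.

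Worked example at b = 20%:

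- SAP 8.4 rule: 0.20 + 0.80 x 0.10 = 28.0% and 0.20 + 0.80 x 0.22 = 37.6%. The ratio is 37.6/28.0 = 1.34 and the difference is 9.6 points.
- Treatment-emergent over all patients: 0.80 x 0.10 = 8.0% and 0.80 x 0.22 = 17.6%. The ratio is 2.20 and the difference is again 9.6 points.
- Patients normal at entry: 10% and 22%, a difference of 12 points.

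| b | SAP 8.4 rule | Risk ratio | Difference, points | Treatment-emergent, all patients | Risk ratio | Difference, points |
|---|---|---|---|---|---|---|
| 0% | 10.0 vs 22.0% | 2.20 | 12.0 | 10.0 vs 22.0% | 2.20 | 12.0 |
| 2% | 11.8 vs 23.6% | 2.00 | 11.8 | 9.8 vs 21.6% | 2.20 | 11.8 |
| 20% | 28.0 vs 37.6% | 1.34 | 9.6 | 8.0 vs 17.6% | 2.20 | 9.6 |
| 40% | 46.0 vs 53.2% | 1.16 | 7.2 | 6.0 vs 13.2% | 2.20 | 7.2 |

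The difference is the same under both rules because b cancels: [b + (1 - b)p1] - [b + (1 - b)p2] = (1 - b)(p1 - p2). The ratio is not protected in this way. At b = 20%, 20/28 = 71% of the patients counted in the lower-rate arm had the abnormality before treatment.

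**Grade 3-4 rows.** With assumed incidences of 10% vs 5% (ratio 2.00), b = 1% gives 10.9% vs 6.0% (1.83 before rounding) and b = 5% gives 14.5% vs 9.75% (1.49). Where entry limits make b zero at screening, as for grade 3-4 neutropenia and thrombocytopenia, there is essentially no distortion.

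**The case against.** The strongest reply is that the plan already deals with most of this. The same summary shows baseline grades by arm, so the burden at entry is visible. Change from baseline is summarised for every laboratory parameter. Under Protocol 8.3.2.3, laboratory abnormalities that the investigator judges clinically relevant are recorded as adverse events, and they then enter the treatment-emergent tables of SAP 8.1. The table is descriptive, and 8.4 specifies no test for it. Table mock-ups sit in a separate tracker that was not available, so a shift table may exist there.

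Much of this stands and limits the point. It does not close the gap. Group percentages and visit-wise means do not show how many patients worsened in grade, and the adverse-event route depends on investigator judgement in an open-label trial. If the tracker already holds a shift table, only the treatment-emergent percentage remains to be added.

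A reader might go further and infer that real arm differences are diluted in general. The documents do not support that: in the model above the absolute difference over all patients is identical under both rules. Only risk ratios, and differences measured against patients normal at entry, are affected. Any loss of power depends on the assumed rates, and no test is planned for this table.

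A reader might also say that the table contradicts the protocol's treatment-emergent definition. That definition governs adverse events, not laboratory tabulations, so the two are inconsistent in approach rather than contradictory.

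**Conclusion.** The point holds in a limited form. The post-dose percentage in SAP 8.4 has no within-patient reference to baseline, so unchanged entry abnormalities are counted as toxicity. Post-dose any-grade rates are overstated and their risk ratios pulled towards 1, mainly for alkaline phosphatase, AST/ALT, GGT, haemoglobin, lymphocytes, glucose and electrolytes. The effect is small for grade 3-4 rows protected by entry limits, such as neutrophils and platelets.

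The size is uncertain. With the assumed 10% vs 22%, the ratio of 2.2 becomes about 2.0 if 2% are abnormal at entry and 1.34 if 20% are. This rests on equal prevalence in the arms, full persistence of baseline abnormalities, and no worsening from a non-zero baseline grade. No prevalence figure is available in the documents. This is a gap in the reporting of safety data; it does not affect the efficacy analyses.

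**What to change.** Keep the current table. In SAP 8.4, for each parameter in Table 6 and for both pools (any grade; grade 3-4), add by arm the percentage of patients whose worst post-first-dose grade exceeds their baseline grade, using the SAP 5.6 safety baseline. State the denominator. Add a shift table of baseline grade by worst post-dose grade for each parameter and arm; this also shows grade 1 to grade 2 worsening.

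In the same edit, say that the post-dose period starts with the first dose of either study treatment, because the present wording refers to the IMP while the protocol calls everolimus the reference product.

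The cost is SAP wording, table shells and a few extra tables. Grades are already to be derived for both periods, so no new data are needed.
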